### **C. Management of Specific Hormonal Therapy Toxicities**

*Note – For management of toxicities listed in this section, study product refers only to hormonal therapy.*

#### **Thromboembolism (VTE)**

Estrogen therapy should not be administered in patients with significant risk factors for or history of venous thromboembolism. Patients suspected of VTE should have estrogen therapy held while they are referred for evaluation. If a VTE is confirmed, estrogen therapy should be discontinued. If no VTE is found, estrogen therapy may be re-initiated in consultation with the CMC.

#### **Hyperkalemia**

Spironolactone potassium-sparing diuretic and mineralocorticoid receptor antagonist that inhibits adrenal aldosterone biosynthesis and can cause elevated serum potassium. For Grade 2 hyperkalemia (5.5 - 6.0 mmol/L), spironolactone should be held and the test repeated within one week of receipt of results. If potassium  $> 5.5$  is confirmed with retesting, spironolactone should be permanently discontinued in consultation with the CMC. If retesting cannot be completed within one week, all attempts should be made by the site to contact the participant for retesting within three additional working days. A participant who fails to undergo repeat potassium testing within one week plus three additional working days will have spironolactone held until results of repeat testing are available.

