### **5.1 Study Product Regimens**

Study product is defined as both PrEP and hormonal therapy.

The PrEP agent in this study will either be Descovy® (emtricitabine 200 mg and tenofovir alafenamide 25mg, FTC/TAF) or Truvada® (emtricitabine 200 mg and tenofovir disoproxil fumarate 300 mg, FTC/TDF) as detailed below.

Country	PrEP Agent	Regimen
U.S.	FTC/TAF 200 mg/25 mg (Descovy ® ) or FTC/TDF 200 mg/300 mg (Truvada ® )	Take one tablet orally once daily
Brazil	FTC/TDF 200 mg/300 mg (Truvada ® )	Take one tablet orally once daily

Estrogen-based hormonal therapy will be consistent with national/international standards such as the World Professional Association for Transgender Health.

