## APPENDIX II: TOXICITY MANAGEMENT

### A. General Guidance:

Guidelines for clinical management and temporary product hold/permanent discontinuation of study product are outlined in this section. In general, the IoR/designee has the discretion to hold study product temporarily at any time if she/he feels that continued product use would be harmful to the participant or interfere with treatment deemed clinically necessary. Unless otherwise specified below, the IoR/designee should immediately consult the CMC for further guidance on resuming study product, continuing the hold temporarily, or progressing to permanent discontinuation of study product. The IoR/designee will document all temporary product holds and permanent discontinuations on applicable eCRFs.

*Management of toxicities under Section A apply to all study products – PrEP and GAHT.*

#### Grade 1 or 2

In general, a participant who develops a Grade 1 or 2 AE, regardless of relationship to study product may continue product use. If the IoR opts to temporarily hold study product, the CMC must be notified.

#### Grade 3

Participants who develop a Grade 3 AE that is judged by the IoR/designee to be unrelated to study product may continue product use but must immediately consult the CMC regarding further management.

For participants who develop a Grade 3 AE that is judged by the IoR/designee to be related to product, study product must be temporarily held until the CMC can be consulted regarding potential resumption or other further management.

If study product is resumed and the same Grade 3 AE recurs at any time during the study, the IoR must consult the CMC for guidance on product use and clinical management. If the Grade 3 AE is deemed related to study product, study product must be temporarily held until the CMC can be consulted regarding permanent discontinuation or other further management.

#### Grade 4

A participant who develops a Grade 4 AE, regardless of relationship to study product, will have the study product temporarily held. The IoR/designee must consult the CMC and continue the temporary product hold until a recommendation is obtained from the CMC. If, in consultation with the CMC, product use is resumed, and the same AE recurs at Grade 4 level at any time during the study, study product must then be permanently discontinued.

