### AST and/or ALT Elevations

Careful assessments should be done to rule out alcohol, non-study medication-related drug toxicity, herbal medications/supplements, or viral hepatitis as the cause of elevation in AST and/or ALT of any grade. The IoR/designee must carefully assess the participant for any symptoms or signs of hepatotoxicity, including fatigue, malaise, anorexia and nausea, jaundice, acholic stools, right upper quadrant pain or hepatomegaly. If the AST and/or ALT elevation is considered most likely to be due to concomitant illness or medication, standard management, including discontinuation of the likely causative agent (if clinically indicated), should be undertaken.

If symptoms or signs of clinical hepatitis are present, the IoR/designee must temporarily hold study product and test the participant for hepatitis (including HBsAg plus any other testing indicated by the local standard of care). If hepatitis B infection is confirmed, consult the CMC.

#### Grade 1

Continue product use and repeat ALT and AST testing within two weeks. Consult with the CMC if there are any safety concern.

#### Grade 2

The IoR/designee must repeat the ALT and AST as soon as possible (at most within 1 week) and then follow the participant weekly until levels are Grade  $\leq 1$ . The frequency of follow up may be altered at the discretion of the IoR/designee following consultation with the CMC. Study product may continue at the discretion of the IoR/designee, provided the participant is asymptomatic. In the case of symptomatic participants, study product will be held temporarily and management (including resumption of study product) should be arranged in consultation with the CMC.

#### Grade 3

The IoR/designee must temporarily hold study product and repeat the ALT and AST as soon as possible (at most within 1 week). The participant should then be followed weekly until levels are Grade  $\leq 1$ , at which point, with concurrence from the CMC, study product may be resumed. If improvement to Grade  $\leq 1$  cannot be documented within three weeks, CMC consultation is required.

If following a Grade 3 event(s) the participant is permitted to resume study product, but has one or more events (AST and/or ALT) at a Grade 3 level, the IoR/designee must perform the following:

- Place a temporary hold on study product
- Offer symptomatic treatment (if appropriate)
- Order any clinically relevant laboratory analyses (per judgment of the IoR/designee)

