### **Creatinine Clearance**

If the participant is using Truvada®, and the creatinine clearance is  $<60\text{mL/min}$ , study product should be held, and the test should be repeated as soon as possible (at most within 1 week of the receipt of the results). If a level of  $<60\text{mL/min}$  is confirmed with retesting, Truvada® study product should be permanently discontinued in consultation with the CMC. If Descovy® is available, the participant should be switched to this medication. If retesting cannot be completed within one week, all attempts should be made by the site to contact the participant for retesting within three additional working days. A participant who fails to undergo confirmatory testing within one week plus three additional working days will require CMC consultation regarding further product management.

If re-testing yields a result  $\geq 60\text{mL/min}$ , the IoR/designee must consult the CMC for further guidance on resuming product use, continuing the hold temporarily, or progressing to permanent discontinuation.

If the participant is using Descovy®, and the creatinine clearance is <30mL/min, study product should be held, and the test should be repeated as soon as possible (at most within 1 week of the receipt of the results). If a level of <30mL/min is confirmed with retesting, Descovy® should be permanently discontinued in consultation with the CMC. If retesting cannot be completed within one week, all attempts should be made by the site to contact the participant for retesting within three additional working days. A participant who fails to undergo confirmatory testing within one week plus three additional working days will require CMC consultation regarding further product management.

If re-testing yields a result  $\geq 30$ mL/min, the IoR/designee must consult the CMC for further guidance on resuming product use, continuing the hold temporarily, or progressing to permanent discontinuation.

If clinical suspicion for renal failure exists, local medical resources with clinical expertise in renal failure must be engaged to the extent available.

NOTE: Adverse events related to creatinine clearance should be based on the assessment of BOTH the absolute creatinine clearance AND the change in creatinine clearance from baseline (Screening Visit). When gradable, only the higher grade of these two assessments should be entered on the Adverse Event e-CRF.

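### The spironolactone hold and one-week retest apply only to an initial potassium of 5.5-6.0 mmol/L, so a higher Grade 3 value judged unrelated carries no required hold, only immediate CMC consultation

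*Combined protocol and SAP*

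**What the plan says.** The potassium rule is in Appendix II, Section C, under Hyperkalemia. Its trigger is: "For Grade 2 hyperkalemia (5.5 - 6.0 mmol/L), spironolactone should be held and the test repeated within one week of receipt of results". If a value above 5.5 "is confirmed with retesting, spironolactone should be permanently discontinued in consultation with the CMC". A participant who has not been retested within one week plus three working days has spironolactone held until a result is available. The rule says nothing about an initial value above 6.0 mmol/L or about Grade 3 or 4 hyperkalemia.

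Appendix II, Section A applies to hormones as well as PrEP: "Management of toxicities under Section A apply to all study products – PrEP and GAHT". This agrees with Section 5.1: "Study product is defined as both PrEP and hormonal therapy". Under Section A:

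- Grade 3, unrelated: "Participants who develop a Grade 3 AE that is judged by the IoR/designee to be unrelated to study product may continue product use", with immediate CMC consultation required.
- Grade 3, related: product is held until the CMC has been consulted.
- Grade 4: "A participant who develops a Grade 4 AE, regardless of relationship to study product, will have the study product temporarily held". The hold continues until the CMC advises. A permanent stop is compulsory only if the same event recurs at Grade 4 after product is resumed.

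**The concern.** A toxicity rule should ask for at least as much at a worse value as at a milder one. Here the specific rule stops at 6.0 mmol/L, and the general rule that takes over is looser in one respect: it lets a relatedness judgement decide whether product continues at Grade 3. The Grade 2 rule does not ask about relatedness at all.

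Section 9.3.3 lists raised potassium as the risk of spironolactone. Under the Schedule of Events (Appendix Ia), potassium is measured at Screening and then quarterly. Without a dated retest, the next scheduled measurement after a high result is nominally 13 weeks away, against one week under the Grade 2 rule. At stake is participant safety and uniform handling across the five sites. No estimate or test in the trial depends on it.

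**Working it through.** No sample size, power or error-rate figure is involved. The check follows an initial potassium result through Section C and then Section A of Appendix II.

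**Step 1. Which values meet the Section C trigger?** The trigger names Grade 2 and prints the range 5.5-6.0 mmol/L. The threshold above 5.5 in the next sentence has no upper limit, but it applies to the retest, which is reached only after the Grade 2 trigger. An initial value above 6.0 therefore does not meet the trigger as written.

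**Step 2. What governs values that do not?** Section A, since it covers GAHT.

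**Step 3. Required actions side by side.**

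| Initial result | Required hold | Retest deadline | Permanent stop on first confirmation | CMC |
|---|---|---|---|---|
| Grade 2 (5.5-6.0) | Yes, any cause | 1 week (+ 3 working days) | Yes, if retest > 5.5 | Consulted on discontinuation |
| Grade 3, unrelated | No | None | No | Immediate consultation |
| Grade 3, related | Yes, until CMC consulted | None | No | Consulted on resumption |
| Grade 4 | Yes, any cause | None | No; only on Grade 4 recurrence | Consulted; hold until it advises |

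Counting the three rows above Grade 2:

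- required hold missing: 1 of 3;
- retest deadline missing: 3 of 3;
- discontinuation on first confirmation missing: 3 of 3.

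The inversion in the hold itself is confined to the Grade 3 unrelated row.

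**Step 4. Is an upper limit the pattern of the appendix?** Four rules in Appendix II use grades or numeric thresholds.

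- AST/ALT: written grade by grade through Grade 4. At Grade 3, without asking about relatedness, "The IoR/designee must temporarily hold study product and repeat the ALT and AST as soon as possible (at most within 1 week"). An unrelated Grade 4 elevation gets the same hold and repeat.
- Nausea, vomiting, diarrhea: the hold starts at Grade 3 and has no ceiling.
- Creatinine clearance: thresholds are open on the side of worsening, for example "If the participant is using Descovy®, and the creatinine clearance is <30mL/min, study product should be held". For Truvada the threshold is below 60 mL/min.
- Potassium: the trigger stops at 6.0 mmol/L, and nothing is written above it.

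Only potassium, 1 of 4, leaves the more severe values without a specific instruction.

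**The case against.** The strongest reply is that the layering may be deliberate. Section A generally lets Grade 1 and 2 events continue product, so a Grade 2 exception is needed for potassium. At Grades 3 and 4, Section A already escalates to the CMC, holds related Grade 3 events and holds every Grade 4 event. The one inverted case is also narrow: a clinician would have to call Grade 3 hyperkalemia unrelated in someone taking a drug that the rule itself describes as able to raise potassium. Other safeguards exist: the investigator may hold product at any time, Section 7.1 has adverse events followed until they resolve or stabilise, and Section 8.9 requires site SOPs on toxicity management. The Grade 2 instruction says should rather than must, and the CMC is also involved in discontinuation at Grade 2.

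Most of this stands as a limit on the harm, and it is why the point is minor. It does not close the gap. Discretion and consultation are not a required hold, and follow-up to resolution has no date. Section 6.4.2 has sites confirm resolution of events that led to a hold, but it accepts clinical assessment or history in place of a laboratory test and does not reach a case in which product was never held. The SOPs and the Study Specific Procedures Manual are not in the documents, so practice may be better than this wording; the finding concerns the wording. The plan gives no reason for asking less at a higher potassium. If Grade 2 was meant as Grade 2 or higher, the printed ceiling of 6.0 says otherwise.

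**Conclusion.** The concern holds as a minor safety wording gap. As written, the potassium rule is stricter at Grade 2 than for a Grade 3 value judged unrelated, and no value above 6.0 mmol/L carries the one-week retest or discontinuation on first confirmation.

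This rests on two points. First, Grade 3 is taken to begin above the printed Grade 2 range; the cut-offs are in the grading table cited in Section 7.5 and are not reproduced in the documents. Second, the number of participants affected is unknown, because no rate of spironolactone use is given. The counts above describe rules, not how often the cases would arise. No endpoint, estimate or analysis is affected.

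**What to change.** In Appendix II, Section C, Hyperkalemia, change the trigger to *Grade 2 or higher hyperkalemia (potassium 5.5 mmol/L or above)*. The hold whatever the cause, the retest within at most one week and discontinuation on confirmation then cover all higher values. Add one sentence stating that, for spironolactone, this overrides the Section A provision allowing product to continue after an unrelated Grade 3 event, and that immediate CMC consultation still applies at Grades 3 and 4. That sentence also keeps the one-week limit from being read as the pace for severe values; any faster action at Grades 3 and 4 is for the sponsor's clinicians to set. In the same edit, align the retest criterion with the trigger, since a retest of exactly 5.5 is now inside the Grade 2 range but below the confirmation threshold.

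The cost is a changed phrase, an added sentence and the aligned retest criterion. No visits or tests are added to the Schedule of Events; the only extra testing is the unscheduled retest for a participant whose potassium is above 6.0 mmol/L.
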